A Markov model will be constructed to evaluate the cost-effectiveness of the use of PGx tests beyond 6 months. The cycle length for the model will be 30 days with a time horizon of one-year. The baseline model population consists of Veterans initiating antidepressant treatment for depression. The respective ages for the baseline model population will be derived from Veterans initiating treatment for MDD in the national VA database so that findings can be generalized to all Veterans. The model structure will be adapted from the study by Perlis et al. [53], which performed cost-effectiveness analyses using a Markov model incorporating probabilities from the multicenter STAR*D effectiveness study of depression. For this study, probabilities from the current trial will be used. Patients will enter the model with a current episode of depression. The first decision node will be whether or not PGx test data are available to the prescribing clinician. Under each study arm, we will develop a state-transition model of probabilities in which an individual patient could occupy a distinct health state, depressed (on treatment consistent with PGx test or on treatment not consistent with PGx test or off treatment), well (on treatment consistent with PGx test or on treatment not consistent with PGx test or off treatment), or death. Probabilities of remission, discontinuation, and recurrence will be drawn directly from the trial and extrapolated to one year. For remitted patients ("well"), the mortality rate will be equal to the age-gender-adjusted all-cause mortality rate from the U.S. Census. For depressed patients, we will add the rate of suicide among depressed patients to the agegender-adjusted all-cause mortality rates of the remitted patients. Costs and utility values will be calculated as described in the section for BIA and CEA studies. For the base case analysis, we will simulate a hypothetical cohort of 10,000 patients using first-order Monte-Carlo simulation. The simulated cohort will have mean demographic characteristics consistent with MDD patients initiating treatment in the VA population nationally. We will perform both 1-way sensitivity analysis on the influential model input parameters (e.g., time horizon, remission, discontinuation, recurrent rates, drug cost, and cost of genomic test) and second order Monte-Carlo simulation by generating 100 cohorts of 10,000 patients to account for potential patient heterogeneity. Since the time-horizon is 1 year, no discounting will be applied.

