5.6.i. Adequacy of sample size. The single primary outcome is a set of repeated binary indicators of remission from depression. As we have a single outcome, we use a Type 1 error rate of 5%. Although we expect the intervention arm to be no less efficacious than the delayed results arm, we use a two-sided test. We also assume a 20% loss to dropout, distributed evenly over time, and across the two groups. The parameters that determine power are the base rate, which is the rate of treatment success expected in the delayed results arm, and the treatment effect. The anticipated remission rate in usual care is based on results from STAR*D [19]. For the base rate, we consider rates of 20-25-30-35%, and for the treatment effect, we look at effects of 5-6-7%. The study design has patients nested within providers, so it is possible that there will be small correlations between the results for two patients of the same provider. Accounting for nesting within provider should also address the nesting within sites [61]. Our design will have approximately 200 providers, with an average of ten patients per provider. The design effect due to provider is then 1+9*r, where r is our assumed provider intra-class correlation. Our sample of size 2000 is then equivalent to an "independent patients" sample of 2000/(1+9*r). We anticipate a low ICC, on the order of r<0.05. If we assume that r=0.05, then the design effect is 1.45, and the effective sample is 1379. For a base rate of 30%, and an assumed within-patient correlation of 0.4 or lower in a compound symmetry structure, then we have 82% power for a 5% treatment effect and 92% for the same effect in an ar(1) structure, with higher power for the same 5% effect with lower base rates. For r=0.01, where we have an effective sample size of 1835, we have power in excess of 90% for 5% effects, under either covariance structure. Even with a conservative estimate of r=0.1, the design effect is 1.9, yielding more than 80% power for treatment effects of 6% or greater.

5.6.j. Data management staffing. [name] and his staff will be responsible to coordinate the various data collection methods used in the clinical trial, and will provide support to the investigators, including site principal investigators to support additional exploratory hypotheses. In this section, we describe the methods that we will use to collect, store, and distribute data from the trial.

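### The Markov base case is one random run of 10,000 patients with no stated limit on simulation error, although the model as described can be evaluated exactly

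*Protocol*

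**What the plan says.** The Markov paragraph of Protocol 5.6.c (Economic evaluation) describes seven states: depressed or well, each on test-consistent treatment, on treatment not consistent with the test, or off treatment; plus death. On timing: "The cycle length for the model will be 30 days with a time horizon of one-year". On the base case: "we will simulate a hypothetical cohort of 10,000 patients using first-order Monte-Carlo simulation". On inputs: "Probabilities of remission, discontinuation, and recurrence will be drawn directly from the trial and extrapolated to one year", and "Costs and utility values will be calculated as described in the section for BIA and CEA studies".

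Two further analyses follow. The first is one-way: "We will perform both 1-way sensitivity analysis on the influential model input parameters", with time horizon, remission, discontinuation, recurrence, drug cost and test cost as examples. The second is a "second order Monte-Carlo simulation by generating 100 cohorts of 10,000 patients to account for potential patient heterogeneity".

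The paragraph is silent on four things: whether 10,000 is the number per arm or in total, whether the two arms use the same random draws, whether one-way runs re-use the base-case draws, and what Monte Carlo error is acceptable. The SAP contains nothing on the economic model.

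**The concern.** Nothing in the description gives a simulated patient a history that alters later transitions. Expected cost and expected QALYs in such a model are obtained exactly by multiplying the state distribution by the transition matrix, cycle by cycle. Drawing individual patients estimates the same mean with error.

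That error matters because the quantity of interest is a small difference between arms, and it sits in the denominator of a ratio. If the error is not small beside the incremental QALYs, the published base-case ratio depends on the random seed. If each one-way run also draws afresh, part of the apparent influence of an input, and so the ranking of inputs, is chance. This is separate from how uncertainty in the trial-derived parameters is handled.

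**Working it through.** The plan states no simulation error and no ratio, so there is no figure to reproduce. The check asks how large the noise would be.

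**Inputs from the protocol.** 10,000 patients, 30-day cycles, one year (12 cycles). From 5.6.i, as a proxy for the transition inputs: "For the base rate, we consider rates of 20-25-30-35" per cent (30% used) and "for the treatment effect, we look at effects of 5-6-7" percentage points (5 used first).

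**Inputs assumed, because the documents give none.** Monthly recurrence 3%; utility 0.6 when depressed; utility gain when well 0.1 to 0.3; mortality 0 or 1% a year. The structure is reduced to depressed, well and dead.

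**Step 1: calibrate.** Week 24 is 168/30 = 5.6 cycles. Monthly remission of 6.70% gives 30% well at that point, and 8.06% gives 35%.

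**Step 2: exact answer.** With w the fraction well, w(t+1) = w(t)(1 - 0.03) + (1 - w(t))p. Averaged over 12 cycles, w is 0.3122 in control and 0.3599 with testing, a difference of 0.0477. Incremental QALYs are 0.1 × 0.0477 = 0.0048 up to 0.3 × 0.0477 = 0.0143.

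**Step 3: simulation error, independent draws, n per arm.** SE = sqrt((SD0² + SD1²)/n).

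- Gain 0.1, no deaths: per-patient SDs are 0.0348 and 0.0354. SE = sqrt((0.0348² + 0.0354²)/10,000) = 0.00050, which is 10.4% of 0.0048 (95%: ±20%).
- Gain 0.1, 1% annual mortality: SDs are 0.0519 and 0.0528. SE = 0.00074, which is about 15.5% (95%: ±30-31%).
- Gain 0.3, 1% annual mortality: about 11% (95%: ±22%).

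A separate run of the full seven-state structure, with its own assumed inputs, gave 10-17%.

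**Step 4: effect on the ratio.** Holding the cost difference fixed, an error of x in the denominator multiplies the ratio by 1/(1 + x).

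| SD of incremental QALYs | 1.96 × SD | Lower limit of ratio | Upper limit of ratio |
|---|---|---|---|
| 10% | 0.196 | 1/1.196, i.e. -16% | 1/0.804, i.e. +24% |
| 17% | 0.333 | 1/1.333, i.e. -25% | 1/0.667, i.e. +50% |

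The seven-state run gave -16% to -25% and +23% to +51% directly.

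**Step 5: what moves the answer.**

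| Setting (no mortality to 1% a year) | 95% noise on incremental QALYs |
|---|---|
| 5 points, independent, 10,000 per arm | ±20-31% |
| 5 points, independent, 5,000 per arm | ±29-43% |
| 7 points, independent, 10,000 per arm | ±15-22% |
| 5 points, shared draws, 10,000 per arm | about ±7% |
| 5 points, shared draws, 5,000 per arm | about ±9-10% |
| 7 points, shared draws, 10,000 per arm | about ±6% |
| 5 points, independent, 1,000,000 per arm | ±2-3% |

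**Step 6: one-way analyses.** 200 repeats, 10,000 per arm, 5 points, utility gain 0.3, no mortality, test cost $2,000 as the only cost difference. Entries are central 95% ranges of the apparent change in the ratio.

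| Input varied | True change | Fresh draws each run | Draws re-used across runs |
|---|---|---|---|
| Test cost +20% | +20% | -13% to +66% | exactly +20% |
| Effect 5 to 6 points | -17% | -32% to +10% | -19% to -13% |
| Recurrence 3% to 4% | +3% | -22% to +35% | -1% to +7% |

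**Step 7: patients needed for a 2% SE.** Independent draws: 10,000 × (10/2)² = 250,000 per arm at a 10% SD, and 10,000 × (17/2)² = 722,500 at 17%. Shared draws: the SE at 10,000 is 6.7/1.96 = 3.4%, so 10,000 × (3.4/2)² is about 29,000.

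**The case against.** Five points deserve weight.

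- **The plan may already pair the arms.** It speaks of one cohort and of a model under each arm, and the budget impact section predicts each participant's cost under both arms. Paired simulation is a fair reading, and it brings the noise down to about ±5-10%. This stands as a possibility, but the text does not say it.
- **There is a larger simulation.** One hundred cohorts of 10,000 make 1,000,000 patients. Pooled, they would average the noise down, and their spread could reveal it. But the stated purpose is heterogeneity, and the plan does not say that this run supplies or checks the base case.
- **Memorylessness is inferred.** The structure is adapted from a cited published model that is not reproduced, and mortality depends on age and sex. Age and sex can be handled by running the matrix within groups. If the final model does need patient history, patient-level simulation has a reason and the exactness argument falls away.
- **Trial sampling error is larger.** With about 1,000 patients per arm, the inputs carry roughly 10,000/1,000 = 10 times the variance of 10,000 simulated patients per arm, ignoring clustering and dropout. True, but that error is unavoidable and belongs in the reported uncertainty; simulation noise is avoidable and shifts the point estimate.
- **It may not change a decision.** In one assumed scenario the exact ratio is $134,000 per QALY and 95% of runs lie between $105,000 and $188,000, all above the protocol's top threshold of $100,000. In another it is about $94,000 with a range of $77,000 to $119,000, which straddles it. Relevance therefore depends on inputs not yet known.

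**Conclusion.** The point holds as a gap in method and specification. The base case uses a noisy estimator where, on the description given, an exact one is available, and the plan sets no number per arm, no rule on random draws and no limit on simulation error. At a 5-point effect with 10,000 per arm and independent draws, the simulation SD is about 10-17% of the incremental QALYs, and the 95% range of the ratio is roughly -15% to -25% / +25% to +50%. With draws shared between arms it is about ±5-10%. These sizes rest on assumed utilities, costs, recurrence and mortality; a smaller true effect would make the relative noise larger.

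Two stronger readings are tempting and not supported. A reader might infer that the ratio will typically move by a quarter to two-fifths. That describes outer 95% limits under independent draws, with inputs that the documents do not give; one standard error is nearer 10-17%. A reader might also infer that the one-way analyses are compromised as planned. That follows only if every run draws afresh, which the protocol neither requires nor excludes.

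The matter is minor. It concerns a secondary economic extrapolation and touches neither primary hypothesis.

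**What to change.** Compute the base case and every one-way run as cohort expected values by transition-matrix multiplication, within age-sex groups if mortality requires it. This removes first-order noise entirely.

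If patient-level simulation is kept because the final model needs patient history, the plan should:

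- state the number of simulated patients per arm;
- use the same random numbers in both arms and across all one-way runs;
- choose enough patients to hold the simulation standard error of the incremental QALYs below a pre-set limit, for example 2%;
- report that standard error beside the ratio;
- say what role, if any, the 100-cohort simulation has in the base-case estimate.

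The only cost is programming, and the matrix version is the shorter program. No trial data, sample size or primary analysis changes.

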5.7 Withdrawal of Subjects

Subjects and providers will be made aware that they may withdraw from this study at any time during the course of the research without penalty or loss of VA or other benefits to which

they are entitled. Given that there are almost no known risks from assessing the PGx profile of a patient, and that the patient will receive usual care throughout his or her study participation, no further procedures for the orderly withdrawal or termination of participation is planned. If a subject withdraws in the control group, the test results will still be returned at the 6 month time point. Withdrawal of the provider has no impact on patient participation.

6.0 Data safety and monitoring plan (DSMP)

Data monitoring. Throughout the trial, we will use an established protocol to manage patients who experience adverse clinical outcomes. Specifically, during the follow-up outcome assessments, there will be a clinical staff member available at all times to call center staff, and patients in significant distress or who have suicidal thoughts (PHQ9 item 9 >1) will speak with a study clinician. The call center clinician will then initiate appropriate care, which may involve initiating a rescue or working with the local investigator to facilitate care. When clinically relevant, we will notify the local site team of the need for further follow-up of the patient. Patients who drop out of care and continue to be symptomatic will be encouraged to reconnect with their clinical team. Patients who report non-adherence to medication or report that they never received their medication will also be encouraged to call their provider. In addition, the local RC will review the chart to ensure that a prescription was written during the time between randomization and the 1 month blood draw or that a note was written indicating why a prescription wasn't written. If neither are found in the chart, the RC will email the provider altering them that the patient did not receive a prescription and query if this was intention or not. Results from the assessments will not be made available in CPRS/VISTA unless required for safety issues or those so indicated at baseline.

Safety review. The DSMP is intended to ensure the safety of research patients and the integrity of the study data. [name], M.D., the Principal Investigator of this program project and [name], will be charged with the duty to receive from sites all submitted adverse events. The individual site investigators will be responsible to report any identified serious adverse events during the recruitment phase and until the 4 week assessment and the Crescenz VAMC site will be responsible to report any adverse events identified during the outcome calls. Given that there are almost no known risks from assessing the PGx profile of a patient, it is anticipated that study-related adverse events will be low. Given that the study population will include patients with serious mental illnesses, adverse events such as hospitalization will occur, but are expected as part of the natural disease course. After assigning causality, the site investigator or the study P.I. or Co-Investigator will decide the course of action for the study patient. The site PI, or for the outcome group, the study Principal Investigator (and, in his absence, Co-investigator) will differentiate serious from non-serious adverse events. Upon discovery, all research-related deaths will be immediately and orally reported to the CIRB and the coordinating center followed by written notification within 5 working days after being made aware of the death. All local serious unanticipated (unexpected) adverse events that are related to the research will be reported to the Central IRB and coordinating center (Crescenz VAMC) within 5 working days. Unanticipated problems that represent a risk to participants and/or others will be reported to the CIRB and the coordinating center within 5 working days. Protocol deviations that substantively affect subjects' rights or safety, or potentially compromise facility human research protection will also be reported to the Central IRB and the coordinating center within 5 working days. An annual report summarizing all adverse events and unanticipated problems/protocol deviations that did not require immediate reporting will be prepared and reported to the Central IRB at the time of continuing review. All reporting requirements as detailed in the VA-CRB-SOP-114 will be followed.

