
Visits 2-6 (Weeks 4, 8, 12, 18, and 24). During treatment, patients will be assessed by centralized assessment center personnel (at the Crescenz VAMC), with all follow-up assessments conducted by telephone. The outcomes assessors will be blinded to the study arm. At each telephone visit, patients' depressive symptoms, medication adherence, and side effects will be assessed. For those participating in the ActiGraph component, we will also ask

about their use of the ActiGraph and any problems they have encountered with the device. Support will be provided as needed. At 36 weeks, we will repeat a final assessment in the delayed results group to test Hypothesis #4 (i.e., that they will ultimately show changes in antidepressant prescribing and reductions in depressive symptoms that are similar in direction and magnitude to those seen in the group that received genetic test results at the outset of the trial). We chose to administer the assessments by telephone centrally because centralized assessment helps to maintain the masking of the treatment condition; enhances consistency in the assessments; allows the use of standardized methods to reach patients, thereby reducing the amount of missing data; and reduces cost. Our group has considerable experience in administering self-assessment instruments by telephone [39, 40]. Outreach efforts will include varying call attempts at different times of the day with one attempt in the evening or on a Saturday, sending a letter, and reaching out to the participant's respective VA site to see whether there is new/additional contact information. Our practice is to call twice, send a letter and then follow with a third call unless instructed differently by the Veteran. We will continue to call up to five times.

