c) CDW: In addition to prospectively collected data, we will require administrative data from the corporate data warehouse (CDW) for both prescribers and patients. The CDW is a representation of the electronic health record. The VA Informatics and Computing Infrastructure (VINCI) is a major informatics initiative of the Department of Veterans Affairs that provides a secure, central analytic platform for conducting research and supporting clinical operations activities. The VA provides services to Veterans at over 1,400 points of care. The electronic health record system used at each point of care is known as the Veterans Information System Technology Architecture (VistA). VistA provides a longitudinal view for patients receiving care nationwide and includes diagnoses, procedures, medications, labs, physiologic measurements, and text notes and reports. Data are aggregated from individual VistA systems to the VA Corporate Data Warehouse, where they are modeled and prepared for use. We will use VINCI to access pharmacy and medical care utilization records for the 12 months prior to study entry, the duration of the study, and the 12 months after the study period. These data will focus on the mental health and substance abuse services delivered to patients and the prescribing practices of prescribers.

d) Assurex outcomes will be received regularly using a VA approved encrypted email method (RMS) or data will be uploaded to a secure Microsoft Teams SharePoint folder managed by Assurex. The data will be uploaded to and stored on secure MIRECC server space. Likewise, biological sample results, and any other source of data will also be stored on secure VA server space with assigned access as need to perform study duties.

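### After week 4 the outcome calls are the only routine source of adverse events, so expected or unrelated serious events in patients who are not reached can be missed

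*Protocol*

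**What the plan says.** Protocol section 6.0, under Safety review, divides routine reporting in two. For the early period, "The individual site investigators will be responsible to report any identified serious adverse events during the recruitment phase" and, continuing the same sentence, "until the 4 week assessment and the Crescenz VAMC site will be responsible to report any adverse events identified during the outcome calls".

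Three further duties in that paragraph carry no week-4 limit:
- For deaths: "Upon discovery, all research-related deaths will be immediately and orally reported to the CIRB and the coordinating center".
- For serious events: "All local serious unanticipated (unexpected) adverse events that are related to the research will be reported to the Central IRB".
- Unanticipated problems that put participants or others at risk, due within five working days.

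The paragraph also states that "adverse events such as hospitalization will occur, but are expected as part of the natural disease course". An annual report summarises the events that did not need immediate reporting.

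Follow-up is by central telephone call at weeks 4, 8, 12, 18 and 24 (section 5.5, Visits 2-6). For patients who are hard to reach there is a letter, calls at varied times and an approach to the patient's VA site for contact details; "We will continue to call up to five times".

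Section 5.5 on data storage says "We will use VINCI to access pharmacy and medical care utilization records", covering the year before entry, the study itself and the year after. The stated uses are medication, service use and the economic evaluation.

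The SAP (Secondary Hypotheses) compares rates of moderate or severe side effects. It plans no comparison of admissions, suicide attempts or deaths.

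**The concern.** A patient who has been admitted, or who has stopped answering, gives no call. If the event is expected or judged unrelated, the text assigns nobody to report it after week 4. A site that learns of a psychiatric admission at week 10 is past its routine window, and because admission is described as expected, the duty covering related, unexpected events would not usually apply.

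The loss may also be informative, since a serious event can itself be the reason a patient stops answering. Patients and providers know their arm, so call completion could differ between arms, although the documents give no evidence that it does. The protocol itself (section 5.6.c, Secondary Responses) treats delayed treatment in the intervention group as a potential adverse outcome, so a harm confined to one arm is conceivable on its own terms. At stake is whether the serious-event count is complete enough to describe safety in a depressed population, and whether the two arms could be compared on it.

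**Working it through.** The plan states no figure on this point, so there is nothing to reproduce. The check has two parts.

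**Which route catches which event after week 4, in a patient who is not reached**

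| Event | Route in the documents | Caught? |
|---|---|---|
| Research-related death | Duty on discovery (6.0) | Yes, if discovered |
| Unrelated death | Early-termination reason (5.5.b); dropout reasons feed safety monitoring (7.0) | Partly; no systematic search |
| Serious event, related and unanticipated | Duty within 5 working days (6.0) | Yes, if discovered |
| VA admission, expected or judged unrelated | None assigned | Can be missed |
| Suicide-related encounter, expected or judged unrelated | C-SSRS, given at baseline and in calls (5.5.b) | Can be missed |
| Non-VA admission, expected or judged unrelated | Self-report in calls (5.5.b) | Can be missed |

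The chart review in section 6.0 does not fill the gap. It checks only that a prescription was written, or its absence explained, by the 1-month blood draw.

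**How much follow-up time is not closed by a call**

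Inputs: 2,000 randomised (section 5.4). Dropout is from section 5.6.i: "We also assume a 20% loss to dropout, distributed evenly over time, and across the two groups". Call weeks are from section 5.5.

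Spreading 20% evenly over five calls gives 4 percentage points per call. Patients missing at weeks 4, 8, 12, 18 and 24 are therefore 80, 160, 240, 320 and 400. An interval counts as not closed when the call that ends it is missed.

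- Weeks 4-8: 4 × 160 = 640
- Weeks 8-12: 4 × 240 = 960
- Weeks 12-18: 6 × 320 = 1,920
- Weeks 18-24: 6 × 400 = 2,400

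Sum: 640 + 960 + 1,920 + 2,400 = 5,920 person-weeks. Total: 2,000 × 20 = 40,000. Share: 5,920 / 40,000 = 14.8%.

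The share is proportional to dropout. An assumed 10% gives 2,960 person-weeks (7.4%) and 30% gives 8,880 (22.2%). If loss is instead taken as continuous and linear and counted from the moment of dropout, 20% gives 400/24 × (24² − 4²)/2 = 4,667 person-weeks, or 11.7%.

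By week 24, 400 patients (about 200 per arm) would have no call.

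**The case against.** The best defence is that the plan is lighter by design and less bare than one sentence suggests. The intervention is a test report, no study drug is given and care is usual care. The events that bear on research risk stay reportable at any time. Early-termination records list death, and dropout reasons go to safety monitoring. Contacting the patient's VA site may bring an admission to light. Section 10.0 adds a safety monitor and mentions a DSMB, and section 6.0 defers to an external procedure that is not among the documents.

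Much of this stands, and it rules out two stronger readings. A reader might infer that nothing need be reported after week 4 unless it comes up in a call; the duties without a time limit contradict that. A reader might also infer that deaths go uncounted; the early-termination route contradicts that, although it is not a systematic search.

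It is also fair that the planned extract is not a ready-made safety dataset. Section 5.5 describes its focus as mental health and substance abuse services. The economic section implies VA inpatient data, but deaths and suicide attempts are not named as items. Non-VA care comes from self-report.

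What the defence does not supply is anyone assigned to report or find an expected or unrelated serious event in a patient who is not reached. The annual report can summarise only what someone has identified, and the approach to the site is for contact details, not events.

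**Conclusion.** The point holds in a limited form. Following the plan as written can under-count VA admissions and suicide-related encounters after week 4 in patients permanently lost to the calls, and it leaves unrelated deaths without a systematic search. A patient who misses one call may report the event at a later one, so intermittent gaps matter less.

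The 14.8% (7.4% to 22.2% for 10% to 30% dropout) is an indication of scale only. It rests on a dropout assumption made for the power calculation and on even loss across the five calls. It measures time not closed by a call; a reader might take it as time with no adverse-event collection, or scale it up by an assumed link between events and loss to get a share of events missed. The documents support neither: other routes remain open, and they give no event rates and no such link, so the number of missed events cannot be computed. Nor do they show that an arm difference has been hidden, since the SAP plans no serious-event comparison in which one could appear.

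This is a cheap improvement to safety ascertainment. It does not affect the primary analyses.

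**What to change.** 1. Amend the Safety review paragraph of protocol section 6.0 so that sites report any serious event they learn of from randomisation through week 24, in both arms.
2. Use the planned VINCI/CDW extract to ascertain serious events for all randomised patients over the same window, identically in both arms and blind to arm. Add fields for admission, emergency visit, suicide-related encounter and death where available. Call reports, including non-VA care, then supplement the extract.
3. Add serious-event counts by arm to the SAP.

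The window must be common to both arms. Only the delayed group has a week-36 call, so its events from weeks 24 to 36 should be reported separately and kept out of the arm comparison.

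The cost is a protocol paragraph, a few extract fields, light review of records for seriousness, and a higher event count to explain. Because the extract runs to a year after the study period, step 2 can also be done retrospectively. Non-VA admissions in patients who are not reached would still be missed, and the report should say so.
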